7.6.3. Extramedullary Disease

Extramedullary disease will be assessed via radiologic imaging studies and evaluation of hepatosplenomegaly on physical exam.

All subjects will have a diagnostic quality imaging study performed during screening to determine the presence of EMD (eg, lymphadenopathy, myeloid sarcoma). Due to the aggressive nature of the disease under study, extramedullary lesions are expected to be avid. As such, FDG PET-CT is the preferred method for detecting and evaluating EMD. Participating investigators who cannot perform PET scans (eg, due to country regulations, institution

capabilities, local standard of care, etc) should still evaluate subjects for EMD by diagnostic quality CT scans with contrast.

Identification and tracking of measureable EMD may more precisely assist in gauging response to treatment. As such, whenever possible, the CT component of the PET-CT scans should be of diagnostic quality and performed with contrast whenever possible.

Subjects who present with EMD at baseline will have follow-up imaging assessments at the following intervals:

- Subjects with baseline PET scans will have a repeat PET scan on Cycle 1 Day 15 (companion CT not required).
- PET-CT or CT scan with contrast in conjunction with the schedule of bone marrow examinations listed above.
- Note the same imaging modality must be used throughout the entire study.

Hepatosplenomegaly will be assessed by palpation on physical exam at baseline and per schedule of assessments.

In subjects who present with lymphadenopathy or other EMD, biopsy is recommended at baseline and at the time of progression.

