APPENDIX E. RESPONSE CRITERIA FOR MYELOID/LYMPHOID NEOPLASMS WITH FGFR1 REARRANGEMENT

Table E1: Response Criteria

Response Subcategory	Response Criteria
CR ^a	
Presence of all of the following improvements:
 
 1. Bone marrow: $\leq 5\%$ myeloblasts (including monocytic blast equivalent) and no lymphoblasts, with normal maturation of all cell lines, and return to normal cellularity^b. 2. Osteomyelofibrosis absent or equal to "mild reticulin fibrosis" (Grade 1 or less fibrosis)^c 3. Peripheral blood^d 
 - WBC $\leq 10 \times 10^9$ cells/L. - Hgb ≥ 11 g/dL. - Platelets $\geq 100 \times 10^9/L; \leq 450 \times 10^9/L$. - Neutrophils $\geq 1.0 \times 10^9/L$. - Blasts = 0%. - Neutrophil precursors reduced to $\leq 2\%$. - Monocytes $\leq 1 \times 10^9/L$. - Eosinophils $\leq 0.5 \times 10^9/L$. 4. Extramedullary disease: Complete resolution of extramedullary disease present before therapy (eg, lymphadenopathy), including palpable hepatosplenomegaly. 
NOTE: Persistent low-level dysplasia is permitted given subjectivity of assignment of dysplasia^b.

PR	
Presence of all of the following improvements:
 
 1. Reduction of bone marrow blasts (and blast equivalents) by 50%, but remaining $> 5\%$ of cellularity (except in cases with $\leq 5\%$ bone marrow blasts at baseline). 2. Normalization of peripheral blood indices listed in CR Criterion 3. 3. Extra medullary disease response of CMR/CR or PMR/PR (see Table E2).
Progression of disease	
Combination of 2 major criteria, 1 major and 2 minor criteria, or 3 minor criteria from following lists:
 
Major criteria:
 
 • Increase in blast counta 
 ○ $< 5\%$ blasts: $\geq 50\%$ increase and to $> 5\%$ blasts. ○ 5%-10% blasts: $\geq 50\%$ increase and to $> 10\%$ blasts. ○ 10%-20% blasts: $\geq 50\%$ increase and to $> 20\%$ blasts. ○ 20%-30% blasts: $\geq 50\%$ increase and to $> 30\%$ blasts. • Evidence of cytogenetic evolution 
 ○ Re-appearance of a previously present or appearance of a new cytogenetic abnormality in complete cytogenetic remission via classic karyotyping or FISH. ○ Increase in cytogenetic burden of disease in partial cytogenetic remission by $\geq 50\%$ via classic karyotyping or by $\geq 50\%$ and involving at least 10% (eg, 2/200) of cells via FISH.

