^c The assessment of CR must be confirmed by a minimum of 2 bone marrow assessments only to confirm improvement in fibrosis. If there is no significant fibrosis present on the initial bone marrow biopsy, then a second biopsy is not required to prove resolution of fibrosis. Grading of fibrosis in measurement of treatment response should be according to the European Consensus System.

^d Resolution of abnormal peripheral blood counts must persist for at least 2 separate analyses over at least 8 weeks. In the case of proliferative disease, CR will include resolution of thrombocytosis to a normal platelet count ($150\text{--}450 \times 10^9/\text{L}$) and resolution of leukocytosis to $\text{WBC} \leq 10 \times 10^9 \text{ cells/L}$ but $\geq 1.5 \times 10^9/\text{L}$. Hemoglobin should be maintained $> 11 \text{ g/dL}$ and platelets $\geq 100 \times 10^9/\text{L}$ without the support of transfusions. Reduction in myeloid precursors (promyelocytes, myelocytes, metamyelocytes, nucleated red blood cells) to less than appreciable levels ($\leq 2\%\text{--}3\%$) and/or $1 \times 10^9/\text{L}$ monocytosis and/or eosinophils $\leq 0.5 \times 10^9/\text{L}$ in the absence of infection, cytokine treatment, or other reactive causes.

^e Transfusion dependency is defined by a history of at least 2 U of red blood cell transfusions in the past month for a hemoglobin level $< 8.5 \text{ g/dL}$ that was not associated with clinically overt bleeding. Cytopenias resulting from therapy should not be considered in assessment of progression.

^f Loss of cytogenetic burden of disease by (via FISH or classic karyotyping) is required to reach complete cytogenetic response. Decrease in the cytogenetic burden of disease must be by $\geq 50\%$ (via FISH or classic karyotyping) to be indicative of a partial cytogenetic response. Given variability of fluorescent probes used in FISH, cytogenetic normalization via FISH will depend on the performance characteristics of the specific probes used.

Table E2: Extramedullary Disease Response Criteria

Assessment	PET-CT Based	CT Based
CMR/CR		
Target	A 5PS score of 1, 2, or 3, w/ or w/o residual mass. Additionally, if screening FDG-PET scan is missing & on-study 5PS score is 1-3, then CMR is possible.	Nodal: < 1.5 cm in LDi. Extra-nodal: Absent.
Non-target		Absent.
New lesions	None.	
PMR/PR		

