Target	5PS score of 4 or 5 with reduced FDG uptake compared to baseline and residual masses of any size. Note: Reduced uptake defined as $\geq 25\%$ decrease in $\% \Delta \text{SUV}_{\text{max}}$.	$\geq 50\%$ decrease from baseline in SPD of all target lesions.
Non-target		No increase.
New lesions	None.	
NMR/SD		
Target	5PS score of 4 or 5 with no significant change in FDG uptake compared to baseline and residual masses of any size. Note: "No significant change in uptake" defined as the criteria of PMR/PMD not being met.	$< 50\%$ decrease from baseline in SPD of all target lesions. No PD criteria met.
Non-target		No progression.
New lesions	None.	
PMD/PD		
Target	5PS score of 4 or 5 with significant increase in FDG uptake, defined as $\geq 50\%$ increase in the $\% \Delta \text{SUV}_{\text{max}}$ of the most FDG-avid disease.	Node or lesion must be abnormal with an LDi > 15 mm, an increase by $\geq 50\%$ from nadir PPD, and an increase in LDi or SDi from nadir by: 
• At least 5 mm for lesions measuring ≤ 20 mm or• At least 10 mm for lesions measuring > 20 mm.
Non-target		Unequivocal progression.
New lesions	New or recurrent markedly diffuse FDG-avid uptake in the liver or spleen.	
• Regrowth of previously resolved lesions.• New node > 1.5 cm in any axis.• New extranodal site > 1.0 cm in any axis.

5PS = Deauville 5-point scale; CMR = complete metabolic response; CR = complete response; CT = computed tomography; FDG = fludeoxyglucose; LDi = longest transverse diameter of lesion; NMR = no metabolic response; PD = progressive disease; PET = positron emission tomography; PMD = progressive metabolic disease; PMR = partial metabolic response; PPD = product of perpendicular diameters; PR = partial response; SD = stable disease; SDi = shortest axis perpendicular to LDi; SPD = sum of product of perpendicular diameters of multiple lesions; SUV = standardized uptake value.

Table E3: Characteristics of Stable Disease

Characteristic	Criteria
CHR	Peripheral blood normalization as in CR Criterion 3 (Table E1 ; peripheral blood response must be verified at ≥ 8 weeks)

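### Table E2 allows a complete metabolic response without a screening PET, against the same-modality rule, which can over-credit partial response; its PET-CT column also has no category for a new focal lesion

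*Protocol*

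**What the plan says.** Protocol Section 7.6.3 requires a diagnostic-quality imaging study at screening for every subject. FDG PET-CT is preferred, with contrast CT where PET cannot be done. It then fixes the method: "Note the same imaging modality must be used throughout the entire study". The early repeat PET in Cycle 1 is asked only of subjects who had a baseline PET.

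Table E2 in Appendix E (SAP Table A2 is the same in substance) scores extramedullary disease in two columns, PET-CT and CT. In the PET-CT column, CMR is "A 5PS score of 1, 2, or 3, w/ or w/o residual mass" on the Deauville five-point scale (5PS), followed by the sentence "Additionally, if screening FDG-PET scan is missing & on-study 5PS score is 1-3, then CMR is possible". The partial (PMR) and no-response (NMR) rows are defined against baseline uptake: "5PS score of 4 or 5 with reduced FDG uptake compared to baseline and residual masses of any size" and "5PS score of 4 or 5 with no significant change in FDG uptake compared to baseline and residual masses of any size". The only new-lesion entry for progressive metabolic disease (PMD) in that column is "New or recurrent markedly diffuse FDG-avid uptake in the liver or spleen".

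Table E2 reaches the endpoints through item 3 of PR in Table E1, which asks for a complete or partial extramedullary response by Table E2, and through the extramedullary item of clinical benefit in Table E3. CR criterion 4 in Table E1 requires full resolution of extramedullary disease, including a palpable liver or spleen, and does not cite Table E2.

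**The concern.** Under Section 7.6.3, a subject with extramedullary disease and no screening PET has a CT baseline and stays on CT. The added sentence in Table E2 offers another route: score a later PET and, if it reads 1 to 3, call the result CMR. There is then no record that the lesion took up FDG before treatment, so a low score may simply be its untreated state.

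The route also works in one direction. Without a screening PET, CMR can be assigned, but PMR, NMR and uptake-based PMD have nothing to be measured against.

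At stake are the CR/PR rate, duration of response (which starts at the first CR or PR) and the clinical-benefit count. All rest on investigator assessment in an open-label study. The missing PET-CT entry for a new focal lesion is a separate gap. It leaves a plainly unfavourable finding without a category on the preferred modality.

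**Working it through.** The plan's one design figure concerns the primary CR rate, and it reproduces. 46 × 0.90 = 41.4, so about 41 are evaluable. The smallest count with a Clopper-Pearson 95% lower limit above 15% is 12 of 41 (limit 16.1%), and P(X ≥ 12 | n = 41, p = 0.35) = 82.4%, against the stated more than 80%. It neither supports nor weakens this point, which is checked by setting the texts side by side.

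**Step 1. What each PET-CT row needs.**

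| Row | Target-lesion rule | Earlier PET needed? | New-lesion entry |
|---|---|---|---|
| CMR | 5PS 1–3, residual mass allowed | No | None allowed |
| PMR | 5PS 4–5, uptake down ≥ 25% | Yes, baseline | None allowed |
| NMR | 5PS 4–5, neither PMR nor PMD met | Yes, baseline | None allowed |
| PMD | 5PS 4–5, uptake up ≥ 50% | Yes | Diffuse liver or spleen uptake only |

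Without a screening PET, the only target-lesion row with a usable definition is the most favourable one.

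**Step 2. One lesion, two columns.** Take a subject with a screening CT, no screening PET, and a target lesion whose size does not change.
- CT column: the change in summed products is 0%, short of the 50% decrease needed for PR, and no progression criterion is met. The category is stable disease.
- PET-CT column with an on-study 5PS of 2: the category is CMR, because a residual mass is allowed.

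**Step 3. Carry it to the endpoints.** PR in Table E1 needs three items: marrow blasts, blood counts and extramedullary response.
- If the subject already meets the first two, stable disease on CT fails item 3 and the subject is not a PR. CMR passes item 3 and the subject is a PR.
- If either of the first two fails, the switch does not change the response. It can still supply one of the two items needed for clinical benefit in Table E3.

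**Step 4. Size.** The change in the response rate is k/N, where k is the number of subjects reclassified.
- With N = 46 (planned), k = 1 gives 1/46 = 2.2 percentage points.
- With N = 47 (treated by 16 April 2023, protocol Section 1.3.2), it gives 1/47 = 2.1 points.
- The FDA efficacy population in SAP Section 5.3.1 is limited to subjects with prior systemic therapy. If it is smaller, each subject weighs more.
- The documents give no count of subjects with extramedullary disease and no screening PET, so k is unknown and no total can be stated.

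**Step 5. New focal lesion on PET.** CMR, PMR and NMR each exclude new lesions, and the PMD entry covers only diffuse liver or spleen uptake. A new focal FDG-avid node or mass therefore fits no PET-CT row. The CT column does cover new lesions (node > 1.5 cm, extranodal site > 1.0 cm). Protocol and SAP carry the same PET-CT cell, so a cell cut short in extraction is unlikely.

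**The case against.** The best defence of the missing-PET sentence is that CMR is an absolute on-study score for everyone. The sentence does not lower that threshold, and it says only that CMR is possible. A mass unchanged on CT can also be CMR in a subject who did have a screening PET. This stands as far as it goes. But with a screening PET, baseline uptake is on record, every row can be assigned and the modality has not changed. None of that holds without one, and the table does not say when the permission applies.

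The Central Review Committee also adjudicates response by baseline disease category (protocol Section 7.6), and SAP Section 7.4 reports its results. Its charter, which is not among the documents, may settle these details. That is real mitigation, but the stated response-rate endpoint rests on investigator assessment.

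A reader might infer more than the documents support:
- **That the primary CR rate is inflated.** Not shown. CR criterion 4 does not cite Table E2. Protocol Section 1.1.2 does say modified Lugano criteria are used for extramedullary response, so an effect cannot be excluded either.
- **That responses have in fact been over-credited, by some stated range.** No count of affected subjects exists, and PR also needs the marrow and blood items.
- **That there is no rule for liver and spleen.** There are rules under CR criterion 4, under progression in Table E1 (palpation thresholds) and under PMD.
- **That an unchanged spleen passes PR in a subject with splenomegaly only.** Item 3 and Section 7.6.3 can equally be read to mean PR is not met. The text is ambiguous.
- **That a new focal PET lesion inflates response or is lost as progression.** It blocks CMR, PMR and NMR, and Table E1 counts new extramedullary disease outside the spleen as a major criterion whatever the scanner. One major criterion alone is not progression, but that is so for CT as well.

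**Conclusion.** The missing-PET sentence conflicts with the same-modality rule and can turn stable disease on CT into the extramedullary response that PR and clinical benefit rely on. The possible bias runs towards a higher CR/PR rate, more subjects entering the duration-of-response analysis, and a higher clinical-benefit count. Its total size cannot be given; per subject it is 2.2 points if N = 46. This assumes that a subject without a screening PET does have the screening CT that Section 7.6.3 requires, and that the marrow and blood items of PR are met.

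The new-focal-lesion gap is real within the PET-CT column. It leaves classification to judgement and is not shown to inflate any endpoint. Both matters concern secondary or supportive results and are worth correcting; neither is shown to touch the primary analysis.

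**What to change.** In both Table E2 and SAP Table A2, before database lock:

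1. Delete the missing-PET sentence, and state that subjects without a screening PET are scored by the CT column throughout, in line with Section 7.6.3.
2. Under PET-CT PMD, state that a new focal FDG-avid lesion attributable to the disease, or a new lesion meeting the CT-column sizes, counts as a new lesion.

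Re-derive the extramedullary categories from data already planned for SAP Listings 2.6.5 to 2.6.8 and 2.6.12. Because most or all subjects have already been treated, report the CR/PR rate, duration of response and clinical benefit under the tables as written and as amended, so that the change is visible.

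Two passages also need reconciling, and no threshold is proposed here. PR item 3 should say how palpable hepatosplenomegaly, which Section 7.6.3 counts as extramedullary disease, is handled. PR item 3 in SAP Table A1 points to a Table D2, while the SAP's own table is A2.

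The cost is appendix wording in two documents and some reprogramming. No new scans are needed. Where the CT part of an on-study PET-CT was not of diagnostic quality, the CT column may not be derivable for that visit, and this should be reported. The reported CR/PR rate may fall slightly.

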APPENDIX F. COVID-19 PANDEMIC MITIGATION STRATEGIES AND INSTRUCTIONS

The COVID-19 global pandemic presents numerous challenges to the ongoing conduct of clinical trials. In line with the European Medicines Agency's Guidance on the Management of Clinical Trials During the COVID-19 (Coronavirus) Pandemic (2020), the sponsor has issued the following Protocol considerations to ensure subject safety is maintained and adequate benefit/risk analyses are applied relative to the completion of study procedures and maintaining the investigational product supply chain.

Recognizing the flexibility required to manage the impact of the pandemic on this clinical trial, additional details will be added to respective study manuals, project plan documents, and communicated to the investigative sites as needed.

Study Site Visits

If local travel restrictions, isolation requirements, or the investigator's benefit/risk assessment determines it to be unsafe for subjects to attend study visits at the investigational site, the site staff may elect to pursue the following:

- In order to minimize subject risk, study visits may be conducted via telemedicine modalities (phone or video). At a minimum, a review of AEs, concomitant medications, and study drug compliance must be completed. Periodic on-site visits should be conducted whenever feasible.
- In order to support investigator oversight of subject safety and disease management, the subject may be asked to perform some laboratory tests or study procedures (eg, eye exam) in a local (proximate) hospital laboratory or facility closer to the subject's residence rather than at the investigational site. In this case, the study physician will provide the subject with the list of parameters to be checked. These tests should be carried out in certified laboratories.

Investigational Medicinal Product Dispensation and Distribution

In order to ensure the continuity of providing their subjects' clinical supplies within the constraints imparted by the pandemic, the site staff can decide to supply IMP to subjects as follows:

- Where possible, when the subject attends a visit at the study site, the investigator can dispense an additional amount of pemigatinib tablets to cover a longer interval between on-site study visits than stipulated in the schedule of assessments (see [Table 4](#)).
- Alternatively, if the subject cannot attend a visit at the study site, adequate supplies of IMP to cover 1 or more cycles can be shipped to the subject by the investigator or appropriately delegated staff (eg, the study pharmacy staff) using a third party service if duly authorized by the subject. The study site may use their own preferred courier, provided the courier adheres to certain standards (eg, use of personal protection equipment, maintenance of temperature-controlled transit environment), or one centrally contracted by the sponsor.

Clinical Trial Monitoring

Study monitoring visits could be postponed; however, the site monitor will continue to employ off-site monitoring practices such as routine communication methods (eg, phone calls, emails, video visits) with the sites to get information on trial progress, subject status, and information on issue resolution. The study monitor may remotely review data entered into the EDC for accuracy and completeness. Remote source data verification may be implemented with agreement of the principal investigator and institution, as applicable.

If the study site monitor cannot be on-site to carry out the final drug accountability for reconciliation purposes, and the operation cannot be postponed, it may be carried out by a pharmacist from the hospital pharmacy or by the study coordinator/data manager with suitable training. The IMP can be returned to the sponsor by the hospital pharmacy directly, or destroyed in accordance with local practices, if applicable, and with sponsor approval.

Direct Contracts With Third Parties/Specialized Service Companies

If necessary, direct contracts can be established with third-party local physicians to conduct activities related to the clinical management of subjects for whom the investigator is responsible and maintains oversight. In such situations, the investigator is required to provide the local physician with a delegation letter listing all delegated activities. The sponsor, through the study investigator or institution, will reimburse the local physician for the test/procedures conducted outside of the standard of care.

Reimbursement of Extraordinary Expenses

The sponsor will arrange to reimburse subjects for any extraordinary expenses, keeping appropriate documentation as evidence (eg, travel expenses for the local laboratory visit(s), the costs of local [proximate] laboratory tests).

APPENDIX G. PROTOCOL AMENDMENT SUMMARY OF CHANGES

Document	Date
Amendment (Version) 1	09 AUG 2016
Amendment (Version) 2	12 DEC 2016
Amendment (Version) 3	17 MAY 2018
Amendment (Version) 4	22 MAY 2019
Amendment (Version) 5	02 JUL 2020
Amendment (Version) 6	13 JUL 2023

Amendment 6 (13 JUL 2023)

Overall Rationale for the Amendment:

The main purpose of this amendment is to modify the long-term treatment visit schedule to start at Cycle 18 and to update the assessments in post-transplant follow-up period. This amendment also incorporates changes from local adaptations for Germany (Amendment 4-DE), Canada (Amendment 4-CA), and Japan (Amendment 4-JP). Changes from Amendment 5-DE, Amendment 5-CA, and Amendment 5-JP are consistent with the changes in Protocol Amendment 5 (dated 02 JUL 2020). Additional changes are summarized below.

1. Synopsis

Description of change: Updated principal coordinating investigator.

Rationale for change: Coordinating investigator changed from [name] to [name].

2. Synopsis; Section 2.2.3, Exploratory Endpoints; Section 6, Study Assessments (Table 4: Study Assessments); Section 7.7.2, Quality-of-Life Assessment

Description of change: Clarified that quality-of-life assessments will be collected until each subject is on study for at least 12 months.

Rationale for change: To update the length of collection of quality-of-life assessments.

3. Synopsis; Section 6, Study Assessments (Table 4: Study Assessments; Table 5: Laboratory Assessments); Section 6.4.2.1, Post-Transplant Follow-Up; Section 7.6.2, Bone Marrow Exams and Cytogenetics (Table 7: Bone Marrow Exam Schedule)

Description of change: Clarified that subjects who bridge to transplant should also have bone marrow biopsy and aspirate and peripheral blood smears, CBCs, and differentials at 1 to 3 months and 6 months post-transplant and then as per local standard of care.

Rationale for change: To allow for the assessment of responses post-transplant.

**4. Synopsis; Section 6, Study Assessments (Table 5: Laboratory Assessments);
Section 7.5.6, Laboratory Assessments**

Description of change: Changed to indicate lipid panel will only be analyzed at Cycle 1 Day 1.

Rationale for change: No safety issues identified across studies with pemigatinib and to be consistent with the other pemigatinib Protocols.

5. Synopsis; Section 6.2.1, Long-Term Treatment Visit Schedule

Description of change: Modified the long-term treatment visit schedule to start at Cycle 18 for subjects who meet the Protocol-defined criteria.

Rationale for change: To ease subject burden.

**6. Section 1.1.1, Fibroblast Growth Factor Receptor Inhibition in Oncology;
Section 1.2, Study Rationale; Section 1.3.2, Potential Risks of Pemigatinib Based on Clinical Safety**

Description of change: Updated based on recently published data.

Rationale for change: To update with more relevant publications regarding FGFR inhibition in oncology and incorporate data based on the most recent IB.

7. Section 3.1, Subject Inclusion Criteria (Criterion 1)

Description of change: Language regarding the age of subjects in Japan, which was originally added in Protocol Amendment 4-JP, has been removed.

Rationale for change: Effective 01 APR 2022, the age of adulthood in Japan changed from ≥ 20 years to ≥ 18 years.

**8. Section 3.1, Subject Inclusion Criteria (Criteria 6b and 6c); Appendix B,
Information Regarding Effectiveness of Contraceptive Measures (Canada Only)**

Description of change: Modified language and added Appendix B to require the use of a highly effective method of contraception in combination with an effective method (barrier method) of preventing pregnancy.

Rationale for change: To conform to Canadian Health Authority contraceptive guidance in clinical trials of teratogenic products.

9. Section 4.5, Overall Study Duration

Description of change: Language was added to indicate the potential end of study, which should occur when the last subject enrolled has been followed for 24 months.

Rationale for change: To define the duration of follow-up and potential end of study.

10. Section 4.6, Study Termination

Description of change: Added language specific to Japan.

Rationale for change: PMDA requirement.

11. Section 5.4.3, Management of Hyperphosphatemia

Description of change: Added the recommended phosphate binder for Japan and indicated it is provided by the sponsor.

Rationale for change: To continue providing lanthanum carbonate hydrate after commercially available for hyperphosphatemia associated with FGFR inhibitor-treatment.

12. Section 6, Study Assessments (Table 4: Study Assessments)

Description of change: Tissue sources for the optional EMD biopsy were expanded to include extranodal locations.

Rationale for change: The disease under study may manifest in extramedullary locations beyond the lymph nodes, this update allows for extranodal sites of EMD to be considered for tissue biopsy collection.

13. Section 6, Study Assessments (Table 4: Study Assessments); Section 7.5.4, Electrocardiograms

Description of change: Frequency of ECGs was reduced to every 3 cycles or more often if clinically indicated.

Rationale for change: Based on data from Study INCB 54828-101 ([Gong et al 2022](#)), pemigatinib does not exhibit any clinically significant prolongation of QTc or dose-dependent changes in heart rate. Consistent with other pemigatinib Protocols, the frequency of ECGs was reduced.

14. Section 6, Study Assessments (Table 5: Laboratory Assessments)

Description of change: Clarified that sample collection for correlative assessments will be decreased to the same schedule as bone marrow samples and efficacy assessments.

Rationale for change: To ease subject burden.

15. Section 8.3.1, Definitions

Description of change: The SAE definition criteria were updated to include events that may lead to disability.

Rationale for change: PMDA requirement.

16. Section 8.3.2, Reporting

Description of change: Added language to clarify requirements for the reporting of SAEs to the head of the site and Japanese regulatory reporting.

Rationale for change: PMDA requirement.

17. Section 8.8, Product Complaints

Description of change: Added language to require the site to report medical device-related complaints.

Rationale for change: PMDA requirement.

18. Section 10.1, Investigator Responsibilities

Description of change: Added language to stipulate the record retention period per J-GCP guidelines.

Rationale for change: J-GCP requirement.

19. Section 10.2, Accountability, Handling, and Disposal of Study Drug

Description of change: Added the investigational drug storage manager per J-GCP guidelines.

Rationale for change: J-GCP requirement.

20. Appendix A, Information Regarding Effectiveness of Contraceptive Methods

Description of change: Added language to clarify unapproved contraceptive methods in Japan.

Rationale for change: To clarify the appropriate methods approved in Japan.

21. Appendix F, COVID-19 Pandemic Mitigation Strategies and Instructions

Description of change: Appendix F was added.

Rationale for change: To provide sites with guidance in response to the COVID-19 pandemic.

22. Incorporation of administrative changes. Other regulatory guidance and administrative changes have been incorporated throughout the Protocol and are noted in the redline version of the amendment.

Amendment 5 (02 JUL 2020)

Overall Rationale for the Amendment:

The main purpose of this amendment is to include updated language for comprehensive eye examination, per FDA feedback. Other modifications have been made to include a long-term treatment visit schedule option for subjects with stable response, to update the Protocol with program-level standard language and post-transplant follow-up, and to provide additional language clarifications.

- 1. Synopsis; Section 6, Study Assessments (Table 4: Study Assessments; Table 5: Laboratory Assessments); Section 6.2.1, Long-Term Treatment Visit Schedule; Section 7.5.6.1, Pregnancy Testing**

Description of change: Language was added to provide subjects who have been on study treatment for more than 78 weeks (18 months), have had a stable clinical and cytogenetic response and manageable adverse events the option to extend study visit frequency to every 3 cycles (9 weeks).

Rationale for change: To ease subject's long-term study visit burden.

- 2. Section 5.4.2, Criteria and Procedures for Dose Interruptions and Adjustments of Study Drug; Section 5.4.3, Management of Hyperphosphatemia; Section 5.4.5, Criteria for Permanent Discontinuation of Study Drug**

Description of change: Added pemigatinib program standard language.

Rationale for change: To conform to pemigatinib development standard language.

- 3. Section 6, Study Assessments (Table 6: Required Analytes); Section 7.5.6.2, Hepatitis Screening Tests**

Description of change: Clarified hepatitis screening requirements.

Rationale for change: To clarify Protocol.

- 4. Section 6, Study Assessments (Table 4: Study Assessments); Section 6.4.2.1, Post-Transplant Follow-Up; Section 7.6.2, Bone Marrow Exams and Cytogenetics (Table 7: Bone Marrow Exam Schedule)**

Description of change: Added language regarding standard of care data to be collected following subjects who successfully bridge to transplant. Added language relative to post-transplant efficacy assessments, including bone marrow examinations.

Rationale for change: Post-transplant status data added per FDA request.

Post-transplant bone marrow examinations added at the end of the post-transplant follow-up period to allow for a final comprehensive efficacy analysis.

- 5. Section 6, Study Assessments (Table 4: Study Assessments); Section 7.5.5, Comprehensive Eye Examination**

Description of change: Language added to indicate that OCT is mandatory at baseline and every 3 cycles and EOT as part of the eye examination process.

Rationale for change: Required program-wide per FDA feedback.

6. Synopsis; Section 6, Study Assessments (Table 4: Study Assessments; Table 5: Laboratory Assessments); Section 7.6, Efficacy Assessments

Description of change: Section edited to provide greater detail regarding efficacy assessments.

Rationale for change: To clarify section for investigators.

7. Appendix D, Response Criteria for Myeloid/Lymphoid Neoplasms With FGFR1 Rearrangement

Description of change: Deleted osteomyelosis grading as a criterion for partial response.

Rationale for change: The criterion is not needed in the definition of a partial response.

8. Incorporation of administrative changes. Other minor, administrative changes and clarifications have been incorporated throughout the Protocol and are noted in the redline version of the amendment.

Amendment 4 (22 MAY 2019)

Overall Rationale for the Amendment:

The main purpose of this amendment is to modify the primary and secondary study efficacy endpoints and to revise the proposed response criteria. Other modifications have been made to include treatment-naïve subjects and to update the Protocol with program-level standard language.

1. Synopsis; Section 1.1.2, Myeloid/Lymphoid Neoplasms With FGFR1 Rearrangement; Section 2, Study Objectives and Endpoints; Section 9.2, Selection of Sample Size; Section 9.4.1, Efficacy Analyses

Description of change: The primary efficacy endpoint was modified to include only the proportion of subjects who achieve a complete response. Secondary endpoints measuring the rates of response and cytogenetic response were added, as were secondary endpoints of duration of complete response and duration of response. An exploratory efficacy endpoint to describe potential indicators of clinical benefit in subjects [REDACTED]

Rationale for change: To evaluate the efficacy of study treatment according to a more conventional endpoint.

2. Appendix D, Response Criteria for Myeloid/Lymphoid Neoplasms With FGFR1 Rearrangement

Description of change: The response criteria table was revised to clarify the groupings of the response categories. Additionally, criterion to evaluate residual fibrosis in the bone marrow was added to the complete and partial response criteria, and the extramedullary disease response criterion was modified in the definition of partial response. Table D2 was added to provide guidance on evaluating extramedullary disease response, and Table D3 was added to list the characterizing criteria of stable disease.

Rationale for change: Criteria have been revised based on investigator and external expert feedback.

3. Synopsis; Section 3.1, Subject Inclusion Criteria

Description of change: Inclusion Criterion 3 was revised to include treatment-naïve subjects who are not current candidates for stem cell transplants or other disease-modifying therapies.

Rationale for change: There is no current standard-of-care therapy to treat the disease under study, and with the clinical activity observed to date, it is worth evaluating treatment with pemigatinib in treatment-naïve subjects.

4. Synopsis; Section 1.3.2.1, Pharmacokinetic/Pharmacodynamic Summary; Section 4.1, Overall Study Design; Section 5.4.4, Up-Titration; Section 6, Study Assessments (Table 4: Study Assessments; Table 5: Laboratory Assessments)

Description of change: Language describing the rationale, criteria, and process for dose up-titration was added.

Rationale for change: To allow up-titration for subjects without hyperphosphatemia due to correlation with low drug exposure.

5. Synopsis; Section 1.3.2, Potential Risks of Pemigatinib Based on Clinical Safety; Section 1.3.2.1, Pharmacokinetic/Pharmacodynamic Summary; Section 5.2.1.1, Description and Administration; Section 5.2.1.4, Instruction to Subjects for Handling Study Drug; Section 5.6.1, Restricted Medications; Section 5.6.2, Prohibited Medications; Section 8.1.1, Definitions; Section 8.1.2 Reporting; Section 8.3.1 Definitions; Appendix B, CYP3A4 Inducers and Inhibitors

Description of change: Study drug administration and handling instructions were updated based on preliminary food-effect study data. Clinical safety, pharmacokinetic and pharmacodynamics data were updated according to the current IB. Language regarding restricted and prohibited medications was updated to align with current program standards. Adverse event definition language was updated according to current company standards.

Rationale for change: To align protocol language with current compound, program, and company standards.

6. Synopsis; Section 6, Study Assessments (Table 4: Study Assessments; Table 6: Laboratory Assessments: Required Analytes); Section 6.4.2, Disease Status Follow-Up; Section 7.6, Efficacy Assessments; Section 7.6.1, Assessment of Disease Response

Description of change: The frequency of disease assessments in the disease status follow-up study period was clarified. Allowance for an automated hematology differential was added. The schedule of bone marrow exams and PET-CT scans was changed to reference weeks on study. The criteria to repeat cytogenetic exams was modified. Clarification regarding recording of flow cytometry data was added. Protocol language relevant to disease imaging studies was clarified. Language regarding the assessment of disease response by investigators and by central review was added.

Rationale for change: To clarify language concerning disease assessments and to introduce language regarding the central review committee.

7. Incorporation of administrative changes. Other minor, administrative changes have been incorporated throughout the Protocol and are noted in the redline version of the amendment.

Amendment 3 (17 MAY 2018)

Overall Rationale for the Amendment:

The purpose of this amendment is to add language to allow for continuous administration of INCB054828. Updated clinical data have been added to support continuous administration. Other modifications have been made based on new preclinical and/or clinical data.

1. Synopsis; Section 1.2, Study Rationale, Section 4.1, Overall Study Design; Section 5.2.1.1, Description and Administration

Description of change: Language has been added to allow for continuous administration of INCB054828.

Rationale for change: Addition of 13.5 mg continuous administration regimen into the study.

2. Synopsis; Section 3.2, Subject Exclusion Criteria

Description of change: Exclusion criteria 3, 14, and 15 have been updated/language refined.

Rationale for change: These criteria have been updated based on new guidelines (criterion 3) and more clinical and preclinical experience with INCB054828 (criteria 14 and 15).

3. Section 1.3.2, Potential Risks of INCB054828 Based on Clinical Safety

Description of change: Updated exposure and safety data from study INCB 54828-101 have been added.

Rationale for change: To provide more safety data for continuous administration of INCB054828.

